5.2.5. End of Study Visit (Week 15 / Day 105 ± 2 days)

This EOS visit applies to all premature discontinued patients and to patients not taking part to the maintenance study. Patients will perform an End of Study Visit (EOS) three weeks after last dosing. Patients will be treated according to the standard of care since the last day of study treatment.

Following examinations/procedures should be performed:

- Physical examination and vital signs;
- Body weight;
- Hematology and Biochemistry panel;
- Blood pregnancy test for all women of childbearing potential;
- Pharmacokinetics blood samples trough levels;
- 12 leads ECG (in case of premature discontinuation only);
- Record any concomitant medications;
- Adverse Events reporting.

NB#1: In case of premature discontinuation occurring during the treatment phase (D1-D84), the above examinations should be performed as an End of Study Visit.

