5.6. Administration and Dosing

5.6.1. Administration of the investigational product

Following randomization, patients will be treated with a daily dose of either 50mg or 100mg ABX464 or will receive placebo.

Treatment groups:

Intervention/treatment Active Arm	
Group #1 (n=20): 100mg qd	2 capsules of 50mg ABX464
Group #2 (n=20): 50mg qd	1 capsule of 50mg ABX464 + 1 capsule of matching placebo
Group #3 (n=20): Placebo	2 capsules of matching Placebo

Patients will be orally dosed in a fed condition (regular breakfast) with a glass of water.

On Day 84 visit, the patient will not take the ABX464-301 study medication (last day of study medication will be on Day 83).

Patient enrolled in the ABX464-302 maintenance study will start the study medication on Day 84 (301 study)/D0 (302 study), ABX464 50mg once daily, right after the study visit.

A paper diary in which the patient should report the number of capsules taken and the intake time from baseline visit onwards, will be given to the patient at baseline.

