6.2 SAFETY SET

The Safety dataset (SAF population) is defined as those patients included in the study, who have received at least one dose of the study treatment.

The Safety Set will be used for all safety analyses.

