11.6 SAFETY ANALYSES

11.6.1 Adverse Events

An overall summary table will be presented (any adverse event, any treatment emergent adverse event (TEAE), any serious adverse event (SAE), death, any grade 3 or higher adverse events from baseline to the end of Study) (*Table 14.3.1.1*). This analysis will be conducted on SAF population.

Primary safety endpoint, the rate of all treatment emergent adverse experiences, will be compared in subjects who received a given dose of ABX464 or placebo by likelihood ratio chi-square test on a 10% two-sided significance level (*14.3.1.2.1*).

Two periods will be defined for TEAE:

- Period I: any adverse event which occurs or worsens from first dosing to Day 84;
- Period II: any adverse event which occurs after Day 84.

Adverse events will be described by primary system organ class and preferred term according to the two periods. Numbers and percentage of patients, and number of occurrences of adverse event will be presented for:

- TEAE (Table 14.3.1.2.2 and Table Table 14.3.1.2.3);
- Serious TEAE (Table 14.3.1.3.1 and Table Table 14.3.1.3.2);
- TEAE leading to drug discontinuation (Table 14.3.1.4.1 and Table Table 14.3.1.4.2);
- TEAE of grade 3 or 4 (Table 14.3.1.5.1 and Table Table 14.3.1.5.2);

Further assessment of safety will be based on the frequency of adverse events (with and without regard to causality) graded according to the CTC-AE Classification and also, the review of individual values for clinical laboratory data, vital signs and ECG focusing on the detection of abnormal values and PCSAs [potentially clinically significant abnormalities (PCSAs) determined upon investigator considerations].

Adverse events will be tabulated (counts and percentages) by group. All adverse events will be listed, and the data will be tabulated by body system/organ class. Adverse event tabulations will include all treatment emergent adverse events, which will be further classified by severity, and relationship to treatment and dose level.

All adverse events (AE) will be classified using the version of the MedDRA coding dictionary specified in the DHM.

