Table 14.3.1.4.2	Treatment-Emergent Adverse Events Leading to Study Drug Discontinuation, by SOC and PT: Period 2	Safety Set
Table 14.3.1.5.1	Treatment-Emergent Adverse Events of Grade 3 or 4 by SOC and PT: Period 1	Safety Set
Table 14.3.1.5.2	Treatment-Emergent Adverse Events of Grade 3 or 4 by SOC and PT: Period 2	Safety Set
Table 14.3.2.1	Listing of Deaths	Safety Set
Table 14.3.2.2	Listing of Serious Adverse Events	Safety Set
Table 14.3.2.3	Listing of Withdrawals Due to Adverse Events	Safety Set
Table 14.3.3.1	Summary of Laboratory Parameters: Haematology	Safety Set
Table 14.3.3.2	Summary of Laboratory Parameters: Biochemistry	Safety Set
Table 14.3.3.3	Listing of Abnormal Laboratory Values	Safety Set
Table 14.3.4	Vital Signs	Safety Set
Table 14.3.5	Shift Table of Physical Examination	Safety Set
Table 14.3.6	Electrocardiogram	Safety Set
Table 14.3.7	Study Drug Exposure and Compliance	Full Analysis Set

Table 14.3.8	Prior Medications	Full Analysis Set
Table 14.3.9.1	Concomitant Medications	Full Analysis Set
Table 14.3.9.2	Changes in Concomitant Medications	Full Analysis Set

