Table 14.2.5.1 Summary of Patients Achieving Different Responses and Remissions (Efficacy Set 1)

		ABX-464 100mg (N=xx)	ABX-464 50mg (N=xx)	Placebo (N=xx)
ARC20 Response				
Week 2	N	xx	xx	xx
	Rate	xx.x %	xx.x %	xx.x %
	Stratified 95% CI	xx.x % - xx.x %	xx.x % - xx.x %	xx.x % - xx.x %
Week 4	N	xx	xx	xx
	Rate	xx.x %	xx.x %	xx.x %
	Stratified 95% CI	xx.x % - xx.x %	xx.x % - xx.x %	xx.x % - xx.x %
Etc				
Etc				

Source: Listing 16.4.5.3
Path\Filename

Page x/y

Programmer's Note: List of variables consists of ACR20/50/70 response, Categorical DAS28-CRP response, LDA, DAS28-ESR remission, ACR/EULAR remission, SDAI remission, CDAI remission.

This layout also applies to:

Table 14.2.5.2 Summary of Patients Achieving Different Responses and Remissions (Efficacy Set 2)

ABX464-301

ddMMMyyyy

Table 14.3.1.1 Summary of Adverse Events (Safety Set)

	ABX-464 100mg (N=xx)		ABX-464 50mg (N=xx)		Placebo (N=xx)		Total (N=xx)	
	n	N (%)	n	N (%)	n	N (%)	n	N (%)
Any Adverse Event	xx	xx (xx.x%)	xx	xx (xx.x%)	xx	xx (xx.x%)	xx	xx (xx.x%)
Any Treatment-Emergent Adverse Event	xx	xx (xx.x%)	xx	xx (xx.x%)	xx	xx (xx.x%)	xx	xx (xx.x%)
Any Serious Adverse Event	xx	xx (xx.x%)	xx	xx (xx.x%)	xx	xx (xx.x%)	xx	xx (xx.x%)
Adverse Event leading to death	xx	xx (xx.x%)	xx	xx (xx.x%)	xx	xx (xx.x%)	xx	xx (xx.x%)
Any grade 3 or higher Adverse Event	xx	xx (xx.x%)	xx	xx (xx.x%)	xx	xx (xx.x%)	xx	xx (xx.x%)

The table presents number of events (n) and number and percentage of patients (N(%)).
The denominator for each percentage is the number of patients within the column.

Source: Listing 16.2.7
Path\Filename

Page x/y

ABX464-301

ddMMMyyyy

Table 14.3.1.2.1 Analysis of Treatment-Emergent Adverse Events (Safety Set)

		ABX-464 100mg (N=xx)	ABX-464 50mg (N=xx)	Placebo (N=xx)	p-value
Any Treatment-Emergent Adverse Event	N	xx	xx	xx	
	Yes	xx (xx.x%)	xx (xx.x%)	xx (xx.x%)	
	No	xx (xx.x%)	xx (xx.x%)	xx (xx.x%)	
Chi-squared test					x.xxxx

The denominator for each percentage is the number of patients within the column
TEAE rate between treatments is compared using likelihood ratio chi-square test at a two-sided 10% significance level.

Source: Listing 16.2.7
Path\Filename

Page x/y

ABX464-301

ddMMMyyyy

Table 14.3.1.2.2 Treatment-Emergent Adverse Events, by SOC and PT: Period 1 (Safety Set)

	ABX-464 100mg (N=xx)			ABX-464 100mg (N=xx)			Placebo (N=xx)			Total (N=xx)		
	n	N (%)	duration (days)	n	N (%)	duration (days)	n	N (%)	duration (days)	n	N (%)	duration (days)

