Any Treatment-Emergent Adverse Event	xx	xx (xx.x%)		xx	xx (xx.x%)		xx	xx (xx.x%)		xx	xx (xx.x%)	
SOC	xx	xx (xx.x%)	xx.xx	xx	xx (xx.x%)	xx.xx	xx	xx (xx.x%)	xx.xx	xx	xx (xx.x%)	xx.xx
PT	xx	xx (xx.x%)	xx.xx	xx	xx (xx.x%)	xx.xx	xx	xx (xx.x%)	xx.xx	xx	xx (xx.x%)	xx.xx
PT	xx	xx (xx.x%)	xx.xx	xx	xx (xx.x%)	xx.xx	xx	xx (xx.x%)	xx.xx	xx	xx (xx.x%)	xx.xx
SOC Etc	xx	xx (xx.x%)	xx.xx	xx	xx (xx.x%)	xx.xx	xx	xx (xx.x%)	xx.xx	xx	xx (xx.x%)	xx.xx
Etc												

The table presents number of events (n) and number and percentage of patients (N(%)).
The denominator for each percentage is the number of patients within the column.
Duration (days) represents median duration of AEs (from baseline to occurrence).

Source: Listing 16.2.7
Path\Filename

Page x/y

This layout also applies to:

Table 14.3.1.2.3 Treatment-Emergent Adverse Events, by SOC and PT: Period 2 (Safety Set)

Table 14.3.1.3.1 Serious Treatment-Emergent Adverse Events, by SOC and PT: Period 1 (Safety Set)

Table 14.3.1.3.2 Serious Treatment-Emergent Adverse Events, by SOC and PT: Period 2 (Safety Set)

Table 14.3.1.4.1 Treatment-Emergent Adverse Events Leading to Study Drug Discontinuation, by SOC and PT: Period 1 (Safety Set)

Table 14.3.1.4.2 Treatment-Emergent Adverse Events Leading to Study Drug Discontinuation, by SOC and PT: Period 2 (Safety Set)

Table 14.3.1.5.1 Treatment-Emergent Adverse Events of Grade 3 or 4 by SOC and PT: Period 1 (Safety Set)

Table 14.3.1.5.2 Treatment-Emergent Adverse Events of Grade 3 or 4 by SOC and PT: Period 2 (Safety Set)

ABX464-301

ddMMyyyy

Table 14.3.2.1 Listing of Deaths (Safety Set)

Treatment	Patient number	Date of death	Cause of death
xxxxxx	xxx-xxxx	ddMMyyyy	xxxxxxxxxxxxxxxxxxxx
xxxxxx	xxx-xxxx	ddMMyyyy	xxxxxxxxxxxxxxxxxxxx
Etc			

Path\filename

Page x/y

ABX464-301

ddMMMyyyy

Table 14.3.2.2 Listing of Serious Adverse Events

Treatment	Centre/ Patient number	Adverse Event PT SOC	Onset date	Resolution date / ongoing	Outcome	Relationship to study drug	Action taken with study drug	Other action taken
xxxxx	xxx-xxxx	xxxxxxxxxx xxxxxxxx xxxx	ddMMMyyyy	ddMMMyyyy / ongoing	Resolved/ Resolved without sequelae/ Etc	Yes/No	None/ Temporary discontinuation/ Etc	Concomitant medication (CM no.)/ Procedure (PR no.)
		xxxxxxxxxx xxxxxxxx xxxx	ddMMMyyyy	ddMMMyyyy / ongoing	Resolved/ Resolved without sequelae/ Etc	Yes/No	None/ Temporary discontinuation/ Etc	Concomitant medication (CM no.)/ Procedure (PR no.)
		Etc						
Etc								

Path\Filename

Page x/y

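### The Period 2 adverse-event tables divide by the whole Safety Set, although the plan does not settle who is followed after Day 84 or whether events on ABX464-302 drug count

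*SAP*

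**What the plan says.** **Periods and tables.** SAP 11.6.1 splits treatment-emergent events into two periods, the second being "Period II: any adverse event which occurs after Day 84". Four tables report it: 14.3.1.2.3 (all events), 14.3.1.3.2 (serious), 14.3.1.4.2 (leading to drug discontinuation) and 14.3.1.5.2 (grade 3 or 4). All reuse the layout of Table 14.3.1.2.2, with the footnote "The denominator for each percentage is the number of patients within the column".

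**Population.** The tables are run on the Safety Set, as in "Table 14.3.1.2.3 Treatment-Emergent Adverse Events, by SOC and PT: Period 2 (Safety Set". SAP 6.2 defines it: "The Safety dataset (SAF population) is defined as those patients included in the study, who have received at least one dose of the study treatment". No set of patients observed after Day 84 is defined anywhere. SAP 11.6.1 closes the treatment-emergent window at study closure or withdrawal and has no rule for rollover.

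**Follow-up after Day 84.** Three protocol sections bear on this:
- 5.2.5: "This EOS visit applies to all premature discontinued patients and to patients not taking part to the maintenance study". The visit is three weeks after the last dose.
- 6.3: every patient should have the End of Study visit, whether they completed or stopped early.
- 7.4: adverse events are recorded until four weeks after the investigational product is completed or discontinued, with no exception for rollover.

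**Dosing.** Protocol 5.6.1 states that the "last day of study medication will be on Day 83", and that patients entering ABX464-302 begin open-label ABX464 50 mg on Day 84, straight after the visit.

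**Column headings.** The Table 14.3.1.2.2 shell heads both active columns "ABX-464 100mg (N=xx"; no column is headed 50 mg.

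**The concern.** A percentage of patients with a late event is readable only if the denominator consists of patients in whom a late event could have been seen. Here the denominator is everyone dosed, while the set of patients observed after Day 84 depends on who chose to roll over and who stopped early. Both may differ by arm if response or tolerability differs. An arm whose patients mostly roll over would then show few late events because few patients were watched.

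The reverse problem arises if rollover patients' events are collected. From Day 84 those patients take open-label ABX464 50 mg, yet the tables place them in the randomised column, so a former placebo patient's event on active drug would count as a placebo event.

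The trial's primary objective is safety at two doses against placebo, and these are the only planned summary tables of events arising after treatment ends.

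**Working it through.** The plan states no figure for Period 2 rates or denominators, so there is none to reproduce.

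**Inputs.** Arm size 20 (SAP 3.3); last planned dose Day 83 (Protocol 5.6.1); End of Study visit at last dose + 21 days (5.2.5); event recording to last dose + 28 days (7.4). The number rolling over, and the number and timing of early stops, are not in the documents. Assumed ranges: 0 to 16 of 20 rolling over, 0 to 4 of 20 stopping early, stop days spread evenly over Days 0 to 83.

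**Formula.** Printed percentage = events / 20. At-risk percentage = events / (number followed after Day 84). Hence printed = at-risk × (number followed / 20).

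**Early stoppers without follow-up after Day 84.**
- By the End of Study visit: last dose + 21 ≤ 84, so last dose on or before Day 63. That is 64 of 84 possible days, or 76%.
- By the four-week recording window: last dose + 28 ≤ 84, so last dose on or before Day 56. That is 57 of 84 days, or 68%.

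**Restrictive reading (Protocol 5.2.5: rollover patients not followed), no early stoppers.**

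| Rolling over | Followed | Printed / at-risk | One patient with an event: printed | At-risk |
|---|---|---|---|---|
| 4 of 20 | 16 | 0.80 | 5% | 6.25% |
| 10 of 20 | 10 | 0.50 | 5% | 10% |
| 16 of 20 | 4 | 0.20 | 5% | 25% |

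With 2 early stoppers, of whom about three quarters (1.5) are unfollowed, the ratios become 14.5/20 = 0.725, 8.5/20 = 0.425 and 2.5/20 = 0.125.

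*Unequal rollover.* Take a true at-risk rate of 20% in two arms. If 16 of 20 roll over, the table prints 20% × 4/20 = 4%. If 10 of 20 roll over, it prints 20% × 10/20 = 10%. The arms look different with no difference in risk.

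**Inclusive reading (Protocol 6.3 and 7.4: rollover patients followed).** Only early stoppers are lost, about two thirds of them by the four-week window:
- 0 of 20 stopping: ratio 1.00.
- 2 of 20: (20 − 1.33)/20 = 0.93.
- 4 of 20: (20 − 2.67)/20 = 0.87.

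The shortfall is 0 to 13%. However, collection then runs to Day 83 + 28 = Day 111, and for rollover patients all of that time is on open-label ABX464 50 mg. Their events enter the 100 mg, 50 mg or placebo column by randomisation. The size and direction of that error cannot be computed from the documents.

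**Discontinuation table.** "Treatment-Emergent Adverse Events Leading to Study Drug Discontinuation, by SOC and PT: Period 2" needs an event with onset after Day 84 that leads to stopping a drug whose last dose was on Day 83. It should be essentially empty.

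**The case against.** The best defence is that an all-treated denominator is a legitimate convention and the footnote discloses it. The Period 2 tables carry no test and print patient and event counts beside the percentages. Table 14.1.3 counts patients who had the follow-up visit, Listing 16.2.1.1 gives last-dose dates and follow-up completion, and Listing 16.2.7 gives onset dates, so a reader could approximate an at-risk rate.

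Part of this stands: nothing is concealed, and no formal comparison is affected. But Table 14.1.3 does not supply the missing denominator, because an early stopper whose End of Study visit fell before Day 84 also counts there as completed. The defence also leaves open whether events on ABX464-302 drug belong in the tables.

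A reader might go further than the documents allow in four ways:
- *Rollover patients have no follow-up after Day 84, so late rates are too low in every arm.* Protocol 5.2.5 supports this, but 6.3 and 7.4 point the other way. Under those sections the main fault is misattribution, and understatement in every arm is not assured.
- *Most early stoppers are unfollowed.* This holds if stopping is even or front-loaded over the 12 weeks, but no stop times are given.
- *The doses cannot be told apart in the primary safety data.* The primary test table, 14.3.1.2.1, is correctly headed 100 mg, 50 mg and placebo. SAP 15 allows layout changes and SAP 12 requires independent quality control. The duplicate heading is a slip in one shell, though seven further tables reuse that shell.
- *Table 14.3.1.4.2 must go.* An essentially empty table does no harm.

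**Conclusion.** The concern holds in a limited form. The Period 2 percentages cannot be interpreted as planned, whichever protocol section governs. Under 5.2.5 they are the at-risk rate multiplied by the share followed, 0.80 down to 0.20 for an assumed 20% to 80% rollover, and arms with different rollover are not comparable. Under 6.3 and 7.4 the dilution is at most about 13% for up to 4 assumed early stoppers of 20, but open-label events are credited to the randomised arm. Every magnitude rests on assumed rollover and stopping patterns.

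The primary treatment-emergent event table and the Period 1 denominator are not in question here. The column heading is clerical.

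**What to change.** 1. Reconcile Protocol 5.2.5, 6.3 and 7.4 on whether ABX464-301 adverse events are collected after Day 84 in patients who enter ABX464-302.
2. In SAP 11.6.1, count in Period 2 only events with onset after Day 84 and before any first ABX464-302 dose. List later events separately, so that nothing recorded is lost.
3. For Tables 14.3.1.2.3, 14.3.1.3.2 and 14.3.1.5.2 (and 14.3.1.4.2 if kept), set N to Safety Set patients with at least one day of such follow-up, change the footnote accordingly, and print patient-days by arm. Patients who start ABX464-302 on Day 84 then leave both numerator and denominator, so the rule works under either protocol reading.
4. Correct the second active column heading in the Table 14.3.1.2.2 shell to ABX-464 50mg.

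The cost is a small SAP and shell edit and a smaller N in the Period 2 tables. The SAP listings do not show an ABX464-302 entry date, so a rollover flag is needed. The Week 12 visit date can stand in for the first open-label dose, since Protocol 5.6.1 places that dose right after the visit. Patients who do not roll over remain a self-selected group, so these tables stay descriptive.

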16 APPENDICES

16.1 STUDY FLOWCHART

	Screening Period	Study Treatment Period						Follow-up Period
	D-30 to D-1	D0	D7	D14	D28	D56	D84	D105
		W0	W1	W2	W4	W8	W12	W15
Time Window (time between two visits ≤ 30 days)			± 2 days	± 2 days	± 2 days	± 2 days	± 2 days	± 2 days
	Screening	Baseline	V1	V2	V3	V4	V5	EOS
Obtained Informed Consent	X							
Check of IN/EX Criteria	X							
Medical History	X							
Height Measurement (cm)	X							
Body Weight (kg)	X	X	X	X	X	X	X	X
Physical Examination	X	X	X	X	X	X	X	X
Vital signs	X	X	X	X	X	X	X	X
Concomitant Medications	X	X	X	X	X	X	X	X
ECG (12 lead)	X	X					X	X*
Blood Pregnancy test (WOCBP)	X				X	X	X	X
Urine Pregnancy test (WOCBP)		X						
Randomization		X						
ABX464/placebo treatment dispensation		X			X	X		
Hematology + Biochemistry#	X#	X	X	X	X	X	X	X
Blood samples drug PK (pre-dose)				X		X		X**
Blood samples drug PK (1-, 2- & 3- hours post-dose)		X		X		X		
Blood samples for Cytokines (gel tube)		X	X	X	X	X	X	
Blood samples for Cytokines (Truculture® tube)		X				X		
Blood samples for flow cytometry cells count***		X				X		
Blood samples for CRP, ESR	X	X	X	X	X	X	X	
Blood samples for miR-124 (Paxgene® tube)		X				X		
Tender Joint Count (28)	X	X		X	X	X	X	
Swollen Joint Count (28)	X	X		X	X	X	X	
Patient Global Assessment of Disease (PtGA-VAS)	X	X		X	X	X	X	
Patient assessment of Joint Pain (Pain-VAS)		X		X	X	X	X	
Investigator Global Assessment of Disease (PrGA-VAS)		X		X	X	X	X	
Health Assessment Questionnaire – Disease Index (HAQ-DI)		X		X	X	X	X	
Functional Assessment of Chronic Illness Therapy (FACIT)-Fatigue		X		X	X	X	X	
Patient diary (dispensation/check)		X	X	X	X	X	X	
Adverse Events recording	X	X	X	X	X	X	X	X
Follow up Headache Questionnaire in case of persistent headache (see section 5.3.2)			X (throughout the study, if needed)					
Dermatologist consultation in case of skin effect (see section 5.3.2)			X (throughout the study, if needed)					

#Tests of TB, HIV, HCV, HBV only at screening; *ECG at EOS visit in case of early termination only; **trough levels PK samples; ***Only in French Coordinating Investigator's Site; Two visits should not be conducted more than 30 days apart
